Power calculations used a range of 10-year overall survival rates from 70-80%, $\alpha=.05$, and two-sided test. Using distributions in Table 2, there is >80% power to detect a 5% survival difference among groups of different surveillance frequencies. Our stakeholders have indicated this level of survival difference to be meaningful.

Potential problems and alternative strategies:

Although the analysis will stratify by prostate cancer risk status, it is possible that within each

risk strata, patients with clinical and pathological features that are associated with a worse prognosis may be followed more frequently than patients with a better prognosis. One way we have proposed to address this issue is with instrumental variable analysis (Page 11). We will test two commonly-used, potential instrumental variables: region and the provider's most commonly used surveillance regimen (commonly called “provider preference”). Another way to address this in our primary analysis is to account for risk variables (clinical and pathological features) within each risk strata. We will plan to incorporate this in the primary analysis as control variables within the outcome models or within the propensity score model, as appropriate to the research question.

Our definition of comparison groups is based on published recommendations and stakeholder guidance. However, schedules for surveillance PSA tests in this observational cohort may not precisely match the anticipated 3, 6, and 12 month intervals. Multiple classification schemes will be assessed for characterizing the surveillance intervals, as described on page 2. The analysis will be repeated using alternative classification schemes, and sensitivity analyses will be used to determine if there are meaningful differences in the results based on classification of surveillance intervals, and to optimize our classification of surveillance frequency [IR-5].

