Introduction: Patient stakeholders have indicated that increased surveillance testing increases anxiety, and that the quality of life impact from frequent surveillance is important to inform decision-making. *The objective of this aim* is to quantify the impact of different surveillance frequencies from the patient's perspective. Aim 2 meets PCORI methodology standards [PC-3] by capturing patient-reported outcomes when the patient is the best source of information. In addition to anxiety, we will measure health-related quality of life in a population-based cohort of prostate cancer survivors undergoing routine surveillance. The *rationale* for this aim is that successful completion of the proposed research will provide further patient-centered information to inform decision-making. Our use of a population-based cohort facilitates generalizability of study findings to the overall prostate cancer survivor population.

Comparators: Comparison groups are the same as Aim 1. PSA frequency will be similarly defined using medical record abstraction.

Data Source [PC-2]: The North Carolina Prostate cancer Comparative Effectiveness & Survivorship Study (NC ProCESS), PI [name], is a prospective population-based cohort of >1,000 patients with newly diagnosed prostate cancer, enrolled from January 2011 through June 2013.²³ Patients were identified in collaboration with the North Carolina Cancer Registry's Rapid Case Ascertainment system, and all patients were enrolled prior to treatment and actively followed prospectively with repeated collection of patient-reported outcomes data and medical records. The primary goal of NC ProCESS is to compare the effectiveness of different surgery and radiation treatments for prostate cancer; these participants are now receiving routine post-treatment surveillance. As a population-based cohort, NC ProCESS participants have similar characteristics (age, prostate cancer diagnosis, treatment patterns) as prostate cancer patients across the US, and are diverse, with 31% non-Caucasian (including 27% African American). These characteristics make NC ProCESS an ideal cohort to examine patient-reported outcomes.

The data available in NC ProCESS include:

- Already available: information regarding prostate cancer diagnosis, primary treatment received, and comorbidities.
- Will be abstracted from medical records: PSA dates and results, procedures, tests, and treatments.

Outcomes [RQ-6][IR-4][PC-3]:

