From Medical records: age at diagnosis, comorbidities (scored using the validated Charlson index), prostate cancer diagnosis (low, intermediate, high risk), treatments;

From patient report: education, household income, race/ethnicity, insurance, marital status, employment.

Data Analysis [IR-3]: Consistent with prostate cancer HRQOL literature, we will treat each patient-reported outcome measure as a continuous variable. We will model changes in anxiety (primary outcome) and HRQOL (secondary outcomes) from the first time point through 60 months using repeated measures methodology such as generalized estimating equations to examine change over time while controlling for patient related covariates. Models will be estimated using PROC GENMOD (SAS 9.4) with an identity link and normal distribution for continuous variables. Models will account for the covariates described above. For the primary outcome of anxiety, we will compare the overall anxiety score among comparison groups, as well as scores for each of the 3 subscales to determine if there is a particular aspect of anxiety which differs by surveillance frequency. For PCSI, scale scores for sexual, urinary, and bowel function will be compared across groups. For the SF-12, mental and physical component scores will be calculated and compared.

A conceptual diagram (directed acyclic graph) demonstrating the relationship between measured covariates and our selected study outcomes for Aim 2 is provided in Figure 3 below. Of note, we anticipate similar relationships between the categories of variables identified in the “other key covariates” section of the directed acyclic graph below to mirror those in Aim 1 / Figure 2. For ease of interpretation we focus primarily on the relationship between variables unique to Aim 2 in the graphic below.

Figure 3. Directed Acyclic Graph for the Hypothesized Relationship between Selected Study Variables and Outcomes for Aim 2

Footnote: Analyses will be stratified by the type of initial treatment (surgery, radiation) and recurrence risk (low, intermediate, high) and the hypothesized relationships may vary somewhat by each clinical scenario.

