Statistical power: A total of 1,079 participants have completed MAX-PC (primary outcome), PCSI and SF12 (secondary outcomes) at 12 months. If there is attrition of 25% from 12 to 60-month time points, that leaves N=809 with complete data. Using the distributions in Table 2, this sample size provides >90% power to detect a $\frac{1}{2}$ -standard deviation (clinically significant) difference in anxiety among the different surveillance frequency groups. More specifically, a sample size as small as 154 in each group will provide 90% power to detect $\frac{1}{2}$ -standard deviation difference among groups. For secondary outcomes PCSI and SF-12, assuming a standard deviation of 10,^{36,37} we have >90% power to detect clinically meaningful differences (1/2 standard deviation = 5 points) among groups. All $\alpha=.05$; two-sided tests.

Potential problems and alternative strategies: Patients with different baseline HRQOL and anxiety may receive different surveillance frequencies. The longitudinal design of Aim 2 and availability of pre-treatment data allow us to analytically account for these potential differences among comparison groups. We do not have MAX-PC data pre-treatment, but will examine if pre-treatment anxiety (an item on SF-12) differs by surveillance frequency groups. If so, we will adjust for this baseline anxiety measure in data analysis. We will address potential clustering as described on Page 6.

We will evaluate the extent to which attrition impacts our analysis and subsequent interpretation. We have planned multiple sensitivity analyses to ensure the robustness of our findings, including

evaluations of the impact of a hypothetical unmeasured confounder, instrumental variables analysis, stratification and restriction.

C3. Avoidance of bias [IR-3][GM-3][CI-5][CI-6]: The large population cohorts used in Aim 1 and Aim 2 will provide a high level of evidence from real-world settings. The following analytic methods to minimize bias and confounding are consistent with the PCORI Methods Report (“Standards for Causal Inference Methods,” dated 3/15/12) and the recent AHRQ publication, “Developing a Protocol for Observational Comparative Effectiveness Research, A User’s Guide.”

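### The listed Aim 2 covariates carry cancer severity only as a three-level risk group; the within-stratum severity control planned for Aim 1 is not carried over, so some severity-related anxiety could be read as an effect of surveillance.

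*Combined protocol and SAP*

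**What the plan says.** **Aim 1, Potential problems and alternative strategies.** The plan says it is possible that, within each risk stratum, "patients with clinical and pathological features that are associated with a worse prognosis may be followed more frequently than patients with a better prognosis". It names instrumental variables as one response. It then says: "Another way to address this in our primary analysis is to account for risk variables (clinical and pathological features) within each risk strata". It continues: "We will plan to incorporate this in the primary analysis as control variables within the outcome models", and the same sentence allows the propensity score model as the alternative place for these variables. The Aim 1 Covariates section names PSA level, Gleason score and clinical stage individually.

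**Aim 2.** The Comparators paragraph uses the same surveillance groups as Aim 1. Under Covariates, the cancer-related entries taken from medical records are "prostate cancer diagnosis (low, intermediate, high risk), treatments". Under Data Analysis, for the GEE models: "Models will account for the covariates described above". The Figure 3 footnote stratifies by initial treatment and by the same three risk levels.

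**Aim 2, Potential problems and alternative strategies.** This covers baseline HRQOL and anxiety, clustering (by cross-reference to Aim 1) and attrition. It also lists sensitivity analyses: a hypothetical unmeasured confounder, instrumental variables, stratification and restriction. On baseline anxiety it says: "We do not have MAX-PC data pre-treatment, but will examine if pre-treatment anxiety (an item on SF-12) differs by surveillance frequency groups"; adjustment follows only if a difference is found. Severity within a risk stratum is not mentioned.

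**The concern.** The confounding that the plan anticipates for survival arises from how the surveillance groups are formed, and Aim 2 forms them in the same way. The strata are broad: intermediate risk spans T2b-c, PSA 10-20 and Gleason 7, and high risk takes in stage T3 and above, PSA over 20 or Gleason 8-10. A man near the upper end of a stratum may be tested more often and may also be more afraid of recurrence, whatever his testing schedule. MAX-PC has a four-item fear-of-recurrence subscale, so severity has a plausible direct path to the primary outcome.

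The Aim 2 hypothesis is that more testing goes with more anxiety. Uncontrolled severity would probably push the estimate the same way, so an apparent harm of frequent testing could partly reflect worse disease. Stratifying or adjusting by risk group cannot remove differences inside a risk group.

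**Working it through.** **1. The plan's own Aim 2 figures.** 1,079 × (1 − 0.25) = 809.25, so N=809 reproduces. The 154 per group is 19% of 809 (153.7), the smallest low-risk group in Table 2. At 154 per group, a half-SD difference and two-sided α=0.05, the SE is √(2/154) = 0.114. Then 0.5/0.114 − 1.96 = 2.43, which is 99.2% power. The 90% in the plan is therefore met as a lower bound.

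**2. A benchmark for the severity-testing link.** The documents give no within-stratum correlation. Table 2 gives the gradient across risk groups: 4 tests in 19%, 23% and 30% of low-, intermediate- and high-risk men. Treating risk and testing as cut-up normal variables, the latent (polychoric) correlation that best fits Table 2 is 0.09 to 0.11, depending on the assumed risk mix (equal thirds give 0.11; 30/50/20% gives 0.09). I take about 0.1 as a benchmark. It is not a measurement of the within-stratum link.

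**3. Spurious difference with no true effect of testing.** Let r1 be the correlation of residual severity with latent testing intensity and r2 its correlation with MAX-PC. Use the intermediate-risk shares of 18/59/23%, so the cut points are −0.915 and 0.739.

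- Mean latent testing, top 23%: 0.3036/0.23 = 1.320. Bottom 18%: −0.2624/0.18 = −1.458. Gap: 2.778. Middle group: −0.070.
- Spurious difference, 4 or more tests versus 1: r1 × r2 × 2.778 SD.
- Group sizes are 809 × 0.18 = 145.6 and 809 × 0.23 = 186.1, so SE = √(1/145.6 + 1/186.1) = 0.1106.
- Two-group false-positive rate: Φ(d/SE − 1.96) + Φ(−d/SE − 1.96).
- Three-group F test: noncentrality 809 × (r1r2)² × (0.18×1.458² + 0.59×0.070² + 0.23×1.320²) = 636 × (r1r2)².

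| r1 | r2 | Difference (SD) | False positives, 4 or more vs 1 | False positives, three-group |
|---|---|---|---|---|
| 0.1 | 0.1 | 0.028 | 6% | 5% |
| 0.1 | 0.2 | 0.056 | 8% | 7% |
| 0.1 | 0.3 | 0.083 | 12% | 10% |
| 0.2 | 0.2 | 0.111 | 17% | 13% |
| 0.3 | 0.3 | 0.250 | 62% | 51% |

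Simulation agrees within its error; at 0.2/0.2 it gave 0.11 SD, 18% and 14%. The low-risk shares give a gap of 2.828 and the high-risk shares 2.648, so the choice of Table 2 column matters little.

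**4. Cross-check by another route.** Suppose one omitted severity feature raises anxiety by γ SD and its prevalence differs by Δp between the groups, so that bias = γ × Δp. With γ of 0.2 to 0.5 and Δp of 10 to 30 points, the bias is 0.02 to 0.15 SD and the false-positive rate 5.4 to 26.5% (about 162 versus 154 men). Both inputs are assumed.

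**5. Cost of the added covariates.** If they explain a share R² of the variation in exposure, the effective group sizes shrink by (1 − R²). With the low-risk shares and R²=0.3, SE = √(1/(161.8×0.7) + 1/(153.7×0.7)) = 0.1346. Then 0.5/0.1346 − 1.96 = 1.75, which is 96.0% power, against 99.3% at R²=0. At R²=0.5 it is 88.1%.

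These calculations treat the comparison as a single difference in means in the pooled sample, as the plan's power statement does, and not as the full repeated-measures model.

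**The case against.** The strongest case is that the plan already has several defences and that its text may not be complete on this point.

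- The severity statement is hedged and sits in the Aim 1 section. A reader might infer that the plan says worse features drive more testing. It says only that this is possible.
- Aim 1 does not commit to the outcome model alone; control through the propensity score is the stated alternative. C3 applies propensity weighting to Aim 2 and selects variables that predict the outcome or confound the comparison. Instrumental-variable and unmeasured-confounder analyses are also listed for Aim 2. A reader might therefore infer too much from saying that severity is controlled for survival and ignored for anxiety.
- Men were enrolled before treatment, so the SF-12 anxiety item may absorb some fear due to diagnostic PSA, Gleason score and stage.
- The Aim 2 covariate list is introduced as what the data include, and Figures 2 and 3 are not available in the text. Finer severity variables may be intended.
- Table 2 suggests a weak severity-testing link. A residual correlation of 0.2 is about twice the across-group benchmark, and 0.3 about three times.

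Much of this stands and limits the size of the point. It does not remove it. The propensity analyses are sensitivity analyses that balance the measured variables chosen for them. Instrumental variables are exploratory under C3. The SF-12 item is used only conditionally and predates surgical pathology. None of these puts within-stratum severity into the Aim 2 primary model.

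**Conclusion.** The point holds as a gap between the two aims. Taken as listed, the Aim 2 covariates leave in the primary anxiety model a confounder that the plan recognises for the same surveillance groups and plans to control in Aim 1. The likely direction favours the Aim 2 hypothesis.

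The size rests on assumed correlations. Near the Table 2 benchmark (r1 about 0.1, r2 of 0.1 to 0.3) the spurious difference is about 0.03 to 0.08 SD, with 5 to 12% false positives instead of 5%. The 0.2/0.2 case, at 0.11 SD and 13 to 18%, is an upper scenario. The 0.3/0.3 row shows sensitivity only and should not be quoted as expected.

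A reader might go further and infer that a finding of harm in Aim 2 would be an artefact of severity. The documents do not support that: no case in the table reaches the half-SD difference that the plan calls clinically significant. The realistic risk is a small difference that is inflated or wrongly declared significant. The change is worth making because it costs little.

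**What to change.** In the Aim 2 primary GEE models and the Aim 2 propensity score, add diagnostic PSA, Gleason score and clinical stage alongside the risk group. For men treated surgically, add post-prostatectomy pathological features if the NC ProCESS records hold them. One sentence in the Aim 2 problems section should state that the within-stratum control described for Aim 1 applies to Aim 2 as well. If finer severity variables were already intended, that sentence and a fuller covariate list are enough.

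The cost is SAP wording, a few covariates and a small loss of precision: pooled power for half an SD stays above 90% even if the new variables explain 30% of exposure variance.

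Data availability needs confirming. The Aim 2 Data Source section says: "Already available: information regarding prostate cancer diagnosis, primary treatment received, and comorbidities". PSA, Gleason score and stage define the risk groups, so it is reasonable to expect that they are held, but the text does not say so, and it does not say whether surgical pathology is available.

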Primary outcome: Our stakeholders identified anxiety and HRQOL (see below) as potential harms of frequent surveillance. The *validated* Memorial Anxiety Scale for Prostate Cancer (MAX-PC)²⁴ will be used as primary outcome for Aim 2. This instrument contains 18 questions assessing anxiety related to prostate cancer (11 items, total score 0 to 33), PSA testing (3 items, total score 0 to 9), and fear of recurrence (4 items, total score 0 to 12). A higher score in each subscale indicates more anxiety.

Secondary outcomes: Prostate cancer treatments can have detrimental HRQOL effects, including effects on urinary, bowel and sexual function symptoms,²⁵ and global quality of life.²⁶ However, HRQOL outcomes in patients who receive different post-treatment surveillance frequencies have not been previously studied. It is likely (we hypothesize) that more frequent surveillance will detect more recurrences, leading to more procedures and treatments resulting in worse HRQOL.

If indeed more frequent surveillance is associated with worse HRQOL, this is critically important data to inform patients about the trade-offs (potential benefit: improved survival; harm: worse HRQOL) of this decision. We will measure 1) Cancer-specific HRQOL using the *validated*, and well-published instrument Prostate Cancer Symptom Indices (PCSI).²⁷⁻³⁴ PCSI measures treatment-related morbidity,³⁴ and is comprised of scales which measure sexual, bowel and urinary symptoms. In each scale, patient answers are converted to a score from 0 (no symptom) to 100 (maximum symptoms). 2) Global HRQOL will be measured by the *validated* Short-Form 12 (SF-12), one of the most frequently used HRQOL instruments in medicine, and has been used frequently in prostate cancer.³⁵ SF-12 provides the Mental (MCS) and Physical Component Summary scores (PCS), calculated using norm-based scoring, with the mean score 50 and standard deviation 10.^{36,37} A lower score indicates lower HRQOL.

NC ProCESS contains complete PCSI and SF12 data at baseline (pre-treatment), and 12 months after treatment; and MAX-PC data at 12 months. NC ProCESS continues to collect these data at 12-month interval time points. By the end of this proposed study, all participants will complete 60-month (5-year) data collection; these data will be available for Aim 2 analysis.

Covariates [IR-3][CI-4]: Data collected at the time of diagnosis by the NC ProCESS include

From Cancer Registry: county of residence;

[figure not shown]

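### Aim 2 puts the pre-treatment PCSI and SF-12 scores in the outcome series, not among the covariates, and does not say how covariates enter the model

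*Combined protocol and SAP*

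**What the plan says.** All references are to section C2 (Specific Aim 2) unless stated.

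- **Outcome series.** Data Analysis: "We will model changes in anxiety (primary outcome) and HRQOL (secondary outcomes) from the first time point through 60 months". The method named is "generalized estimating equations to examine change over time while controlling for patient related covariates".
- **First time point.** Outcomes: "NC ProCESS contains complete PCSI and SF12 data at baseline (pre-treatment), and 12 months after treatment; and MAX-PC data at 12 months". Collection then continues every 12 months to month 60. PCSI and SF-12 therefore have six time points, the first before treatment. MAX-PC, the primary outcome, has five, the first at month 12.
- **Adjustment.** Data Analysis says "Models will account for the covariates described above". The Covariates paragraph lists county; age, comorbidity, risk group and treatments from records; and, "From patient report: education, household income, race/ethnicity, insurance, marital status, employment". No PCSI or SF-12 score appears. No group-by-time or covariate-by-time term is mentioned.
- **Contrast.** The same paragraph speaks both of modelling change and of comparing scores across groups.
- **The plan's own concern.** Potential problems and alternative strategies: "Patients with different baseline HRQOL and anxiety may receive different surveillance frequencies". It adds that the pre-treatment data make it possible to account for such differences. The only rule given is for one SF-12 anxiety item, which is adjusted for if it differs between groups.
- **Other provisions.** The Figure 3 footnote stratifies by initial treatment and risk group. Section C3 plans propensity weighting (IPTW) and matching as sensitivity analyses.

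**The concern.** A pre-treatment score precedes any surveillance, so surveillance cannot have affected it. The plan suspects that this score influences how often a man is tested, which makes it a candidate confounder, yet the analysis treats it as a response. The text leaves two readings open, and each has a weakness for PCSI and SF-12.

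- **Group-by-time (change) reading.** A covariate measured once and entered as a main effect shifts a man's level equally at every visit and cancels from his change. The contrast could then be reported as adjusted when it is not.
- **Average-level reading.** Covariate main effects do adjust this contrast. However, one of the six averaged values predates exposure.

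At stake is the quality-of-life side of the trade-off that Aim 2 is meant to describe. Men who differ at the start could appear to be helped or harmed by their testing schedule.

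**Working it through.** **1. The plan's own figures.** This point disputes no stated number. 1,079 × 0.75 = 809.25, so N = 809 reproduces. For a 5-point difference with SD 10, two-sided α = 0.05 and the Table 2 shares, the lowest pairwise power at N = 809 is 99.3% (low risk, 1 versus 4 tests, about 162 versus 154 men). The claim of more than 90% therefore holds as a bound.

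**2. Covariate main effects and a change contrast.** The documents give no confounder size, so these inputs are assumed:
- a binary covariate present in half the men;
- probability of frequent testing 35% with it and 15% without it;
- level 3 points lower with it, and 60-month change 4 points worse;
- no true effect of surveillance.

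Overall, (0.35 + 0.15)/2 = 25% are tested frequently. Covariate prevalence is 0.5 × 0.35/0.25 = 0.70 in the frequent group and 0.5 × 0.65/0.75 = 0.433 in the other, a difference of 0.267. Expected bias in change = −4 × 0.267 = −1.07 points. A large simulation with six complete visits gave:

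| Contrast and model | Estimate (truth 0) |
|---|---|
| Group-by-time, no covariate | −1.08 |
| Group-by-time, covariate main effect | −1.08 |
| Group-by-time, covariate-by-time added | −0.02 |
| Group-by-time, IPTW on the covariate | −0.03 |
| Average level, no covariate | −1.34 |
| Average level, covariate main effect | −0.01 |

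The main effect does nothing for the change contrast and corrects the level contrast.

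**3. Baseline score drives surveillance (the plan's own concern).** Assume equal SDs, correlation ρ between any two visits, surveillance depending only on the baseline score, no true effect, and visit treated as categorical. A baseline gap d then leaves an expected gap of ρd at every later visit.

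- Change comparison: ρd − d, a bias of size (1 − ρ) × d, opposite in sign to the gap. For d = 1 and ρ = 0.8 it is 0.2. For d = 3 and ρ = 0.5 it is 1.5. For d = 5 and ρ = 0.4 it is 3.0.
- Six-visit average: (d + 5ρd)/6 = d(1 + 5ρ)/6, with the same sign as the gap. For d = 3 and ρ = 0.5 it is 3 × 3.5/6 = 1.75.

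The two readings would therefore err in opposite directions. A simulation with a gap of about 2.9 points gave change biases of 1.44 (ρ = 0.5) and 0.88 (ρ = 0.7). With baseline as a covariate the biases were −0.03 and 0.00. Covariate-by-time terms for the listed covariates cannot be relied on to remove this bias, because the baseline score is not among them.

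**4. Dilution.** Suppose surveillance has a constant true effect of 5 points from month 12. Averaging it with a pre-treatment value that carries no effect gives 5 × 5/6 = 4.2 points.

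**The case against.** The strongest reply is that this is silence, not error. The plan nowhere says that covariates enter only as main effects. Where it describes comparisons between groups, it refers to scores, and for a level contrast main effects do adjust. It announces an intention to use the pre-treatment data. Stratification lets time trends differ by treatment and risk group, and IPTW can balance a change contrast. Keeping the baseline score in the response vector is an accepted longitudinal model.

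Most of this stands, and it limits what can be claimed:

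- A reader might infer that the plan prescribes main-effects adjustment and so cannot remove confounding. The text does not fix the functional form, so this is one possible reading.
- A reader might add the two harms together. They are alternatives: the unadjusted contrast belongs to the change reading, the dilution to the average reading.
- A reader might extend the baseline-score point to the primary outcome. MAX-PC has no pre-treatment score, so only the covariate-by-visit point reaches it, and only for a change contrast.
- A reader might infer a high false-positive rate. The documents give no confounder size or correlation, and the rate depends heavily on group sizes. With SD 10 and every between-visit correlation 0.5, the standard error of the mean follow-up change is √60 × √(2/404) = 0.54 for two equal groups of 404, but √60 × √(1/162 + 1/154) = 0.87 for the smallest pair in Table 2.

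The reply does not remove the point. The intention to account for baseline differences is not carried into the model or the covariate list. Stratification does not cover age, comorbidity, socioeconomic factors or baseline score. IPTW is a sensitivity analysis, and the pre-treatment scores are not named for its propensity model.

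**Conclusion.** The concern holds for PCSI and SF-12 in a limited form. Their pre-treatment scores fall in the outcome series and off the covariate list, although the plan regards baseline quality of life as a possible cause of surveillance frequency and names no method to handle it. On the change reading with main effects only, the contrast is unadjusted when visits are complete. On the average reading, a true effect shrinks to about 5/6 and baseline imbalance remains.

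If baseline score drives surveillance, the bias in a change comparison is about 0.2 to 3.0 points over the assumed range, against a 5-point meaningful difference. That could distort a result, but the actual size is unknown. The conclusion rests on the plan's own premise that baseline score is a confounder. Stratification and sensitivity IPTW are partial safeguards. This should be corrected before analysis. It is more than a request for detail, because a better use of data already collected is available.

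**What to change.** 1. For PCSI and SF-12, take the pre-treatment score out of the outcome series. Model the 12- to 60-month scores on surveillance group, visit, the pre-treatment score of the same scale and the listed covariates.
2. Name the main contrast: the adjusted group difference averaged over months 12 to 60.
3. Wherever a group-by-visit or change contrast is reported, including for MAX-PC, add covariate-by-visit terms, and baseline-by-visit terms where a baseline score exists. Without them, the group-by-visit terms in the model above would have the same weakness.
4. Name the pre-treatment scores as variables in the propensity model for these outcomes.

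The cost is SAP wording, since the scores are already collected. The downsides are extra parameters and reliance on the premise that baseline score is a confounder. With five follow-up visits, each covariate term interacted with visit adds four parameters. This matters mainly in small strata: six equal strata, an assumption, would hold about 809/6 = 135 men each. Baseline adjustment is not unbiased under every causal structure, so a change analysis with the terms in item 3 is a reasonable sensitivity check.
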